2. To develop and internally validate a model that uses the duration and degree of intraoperative and postoperative hypotension to predict daily probability of MINS or death (binary outcome, according to the 2021 American Heart Association (AHA) definitions (6) from postoperative days zero to two.
3. To evaluate how different definitions of hypotension affect the primary and secondary models above, and analyze the intraoperative and postoperative hypotension separately to determine whether intraoperative or postoperative hypotension alone are sufficient for prediction.
4. To explore whether other intraoperative and postoperative vital sign information (heart rate, oxygen saturation, and end-tidal carbon dioxide derangements at various definitions) add predictive value to the primary and secondary models above.
5. To use machine learning methods to perform exploratory analysis to determine 1) optimal methods for imputation for time series data; 2) visualization of time series data in the setting of prediction; 3) development and internal validation of machine learning models to use the time series data to predict troponin levels; and 4) to determine how many hours earlier than a binary MINS diagnosis were vital signs able

to predict a MINS diagnosis (as determined by when in the time series prior to MINS diagnosis that the model achieved various thresholds of predicted probability).

Methods

This is a single-center, retrospective cohort study on the development and internal validation of a prediction model.

Population

This study will include patients aged 45 years and older undergoing inpatient noncardiac surgery, who had MINS protocol ordered for postoperative high sensitivity troponin monitoring based on the CCS guidelines (5) from January 2020 to June 2021 (estimated sample size of 750, event rate of ~75).

Patients will be excluded if they do not have intraoperative and postoperative vital signs, or any postoperative troponin measurements. Patients who underwent repeat surgery or were readmitted within the first 72 hours postoperatively will be excluded, since patients who are discharged and readmitted will not have vital measurements as outpatients. If a patient had multiple admissions where the MINS protocol was ordered, only the first inpatient admission will be included. Patients who had positive troponin on postoperative day 4 will be excluded, since vital signs are only included up to postoperative day 3 for consistency.

Data sources

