- Modelling using a generalized linear mixed effects model for binary definitions of troponin increase (per AHA, as described above).
 - Different truncations of vital sign data stream prior to MINS diagnosis (e.g. no truncation, 12h before diagnosis)
 - If sample size allows: subgroup analysis involving only patients with preoperative troponin; subgroup analysis for patients who are in the intensive care unit perioperatively, as this represents a sicker population.
- Intraoperative only, postoperative only
- Further inclusion of additional predictors (e.g. % duration of $\text{HR} > 100$) from the available vital signs data
- Exploration of the incremental value of vital signs in addition to the RCRI or NT-proBNP in predicting MINS or myocardial injury
- Inclusion of information from postoperative day 3
- Delta troponin (change from preoperative troponin) using linear contrast

Model evaluation

To validate the performance of the linear mixed effects model specified in the primary statistical analysis plan, given the longitudinal nature of the data, a repeated patient-based 5-fold cross-validation will be performed with 100 repetitions (doi:

10.1093/gigascience/gix019). Patient-based record was chosen as record-wise cross validation tends to overestimate prediction accuracy compared to subject-wise cross validation. Note that when using a linear mixed effects model to predict troponin for “new”

patients (such as those in a held-out validation set), there are no unique random effects corresponding to those patients and so we are assuming the mean response for these “new” patients. A “patient-based” approach for the cross-validation approach is performed to avoid data leakage from the training set into the validation set (i.e. a patient’s measurements could potentially be present in both the training and validation sets). To quantify predictive performance, the root mean square error (RMSE) will be computed for each repetition, and the corresponding average and standard deviation of those performance measures will be reported. Marginal (i.e. fixed effects only) and conditional (i.e. fixed and random effects) R-squared (Nakagawa and Schielzeth R-squared, doi.org/10.1111/j.2041-210x.2012.00261.x) will be calculated. For assessment of calibration, the predicted values will be averaged across all repetitions (for each actual observation), and a calibration plot will be generated along with measures of the calibration intercept and slope.

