For the models involving the binary outcomes of MINS diagnosis, a similar validation approach will be conducted. To assess discrimination, receiver operating characteristic curves (ROCs) will be generated and their area under the curves (AUCs) will be computed for each repetition, forming a distribution of AUCs. Precision-recall curves will also be considered due to the severe class imbalance present in the dataset. Pseudo R-squared will be computed. To assess calibration, the mean predicted class probability will be taken across all repetitions for each observation and then a decile calibration plot will be created, with corresponding calibration intercept and slope.

Decision curve analysis will be done to determine the net benefit of the various binary outcome models across various thresholds, as compared to ordering or not ordering troponin on everyone.

Parameter Count Based on Sample Size and Event Rate

To mitigate potential overfitting of the model onto the available data, we will aim to restrict the number of coefficient terms included within our linear mixed effects model to be at most 15 (i.e. 50 parameters per patient), and 8 variables for the generalized linear mixed effects models (i.e. 10 parameters per outcome event). As there is limited guidance for longitudinal prediction models, this is a choice justified based on a combination of the anticipated sample size, the presence of repeated measures, the modelling of a continuous outcome, the interest in examining interactions between vital signs predictors and the time predictor, and lastly to minimize uncertainty in the predictions.

Approach II. Machine learning exploratory analyses

Aim 1:

We will evaluate several strategies to determine the optimal integration of workflow for imputation and internal bootstrap validation for small medical datasets involving longitudinal data, including modeling vital signs as a time series vs. summary variable. The best performing workflow will be written as a function available on GitHub.

Aim 2:

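### The only spread planned for RMSE and AUC is over re-splits of the same patients; no patient-sampling interval is stated for any performance measure or model difference of the conventional models

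*Combined protocol and SAP*

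**What the plan says.** All places are in the combined protocol and SAP.

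- **Cohort (Population):** "estimated sample size of 750, event rate of ~75".
- **Continuous model (Model evaluation):** RMSE is calculated once per repetition of the cross-validation, and "the corresponding average and standard deviation of those performance measures will be reported".
- **Binary models (Model evaluation):** the validation is similar. ROC curves are drawn and "their area under the curves (AUCs) will be computed for each repetition, forming a distribution of AUCs".
- **Calibration (Model evaluation):** for the continuous model, "the predicted values will be averaged across all repetitions (for each actual observation"; for the binary models, "the mean predicted class probability will be taken across all repetitions for each observation". One intercept and one slope are then calculated from the averaged predictions.
- **Model comparisons:** Objective 3 is "To evaluate how different definitions of hypotension affect the primary and secondary models above", and Objective 4 asks whether other vital signs add predictive value. The secondary analyses list "Exploration of the incremental value of vital signs in addition to the RCRI or NT-proBNP". Primary Modeling also allows the best longitudinal model to be chosen on discrimination and calibration. No interval or test for a difference accompanies any of these.
- **Bootstrap:** the word occurs once, in machine-learning Aim 1 of Approach II, where workflows for "imputation and internal bootstrap validation for small medical datasets involving longitudinal data" are to be evaluated. It is not assigned to the conventional models.

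**The concern.** Every repetition reuses the same patients. The SD of RMSE and the distribution of AUCs therefore measure fold-assignment (Monte Carlo) noise. More repetitions stabilise the mean but carry no information about patient-sampling error. For calibration even the split variability disappears, because predictions are averaged before the intercept and slope are calculated.

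Objectives 1 and 2 are to develop and internally validate models, so the performance estimates are the main result. If the plan is followed as written, the only spread printed beside them is much smaller than their real uncertainty. Objectives 3 and 4 turn on differences between models fitted to the same patients, and no precision is stated for those differences. The plan itself chose the day as its time unit so that readers would not read too much precision into the results. A split SD reported alone works against that aim.

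**Working it through.** **1. The plan's own figures.** The plan gives no figure for precision or interval width. Its only figures tied to sample size are in the parameter-count section: 750/15 = 50 patients per coefficient, which reproduces, and 75/8 = 9.4 events per variable, stated as 10. Neither bears on the precision of RMSE or AUC.

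**2. Sampling error of the AUC, closed form.** Inputs: m = 75 events and n = 750 − 75 = 675 non-events (Population). The AUC value A is an assumption, since the documents expect none.

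Hanley-McNeil: SE² = [A(1−A) + (m−1)(q1−A²) + (n−1)(q2−A²)] / (mn), with q1 = A/(2−A) and q2 = 2A²/(1+A).

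At A = 0.70: q1 = 0.5385, q2 = 0.5765, A² = 0.49.
Numerator = 0.21 + 74 × 0.0485 + 674 × 0.0865 ≈ 62.1 (unrounded terms). Denominator = 75 × 675 = 50,625.
SE = √(62.1/50,625) = 0.035, and 1.96 × 0.035 = 0.069.

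| AUC | SE | 95% half-width |
|---|---|---|
| 0.65 | 0.036 | 0.070 |
| 0.70 | 0.035 | 0.069 |
| 0.75 | 0.034 | 0.066 |
| 0.80 | 0.031 | 0.062 |

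At AUC 0.70, 60 events (690 non-events) give 0.039 and 90 events (660) give 0.032. Counting patient-days instead (750 × 3 − 75 = 2,175 non-event days) gives 0.034. The answer is not sensitive to these choices.

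**3. Split SD against sampling SD of the AUC, by simulation.** The setting was 150 cohorts of 750 patients, eight predictors, 10% events, patient-level logistic regression and repeated five-fold cross-validation. The split SD comes from 100 re-splits in each of 20 cohorts. The sampling SD is the SD of the cross-validated AUC between cohorts.

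| Mean AUC | Split SD | Sampling SD | Ratio |
|---|---|---|---|
| 0.67 | 0.0120 | 0.0374 | 3.1 |
| 0.73 | 0.0095 | 0.0350 | 3.7 |
| 0.78 | 0.0074 | 0.0301 | 4.1 |

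The sampling SDs agree with the closed form. A separate simulation used up to three days per patient, truncation at the first event, the a priori terms and a mean of 74.6 events. It gave a split SD of 0.011 against 0.035 to 0.036, a ratio of 3.1 to 3.4. By contrast, the Monte Carlo error of a mean over 100 repetitions is only about 0.012/√100 = 0.0012, so 100 repetitions do settle the point estimate.

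**4. RMSE, by simulation.** With 750 patients, three days each and a log-scale outcome, RMSE was 0.812, split SD 0.0019 and sampling SD 0.0180, a ratio of 9.4. Sampling error is 0.0180/0.812 = 2.2% of RMSE. A random-intercept version gave a ratio of about 10 with 10 coefficients and about 8 with 15, the plan's cap. On raw right-skewed troponin the ratio ran from 14 to 48, depending on the assumed log-SD (0.52 or 0.94) and on whether RMSE is pooled or averaged over folds.

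**5. Limits.** Effect sizes, variance components and skew are assumptions, because the documents give none. The binary simulations used fixed-effect logistic regression, not the planned mixed model. The plan predicts new patients without their random effect, so ranking rests on the fixed part. The direction was the same in every setting; the exact ratios should not be read as precise.

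**The case against.** **The plan describes its SD correctly.** It reports a mean and SD over repetitions and nowhere calls the SD a confidence interval. It neither plans nor excludes standard errors for calibration. This stands: a reader might infer that the plan presents the SD as sampling precision, and the text does not support that. What remains is that no other measure of precision is stated for the study's main result.

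**No decision rule depends on it.** There is no performance threshold, test or adoption rule, and much of Objectives 3 and 4 is exploratory. This also stands, and it limits severity. A reader might infer that a particular gain from adding hypotension terms would be wrongly declared real. The documents give no expected gain, so no such example can be supported.

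**The RMSE ratio overstates the harm.** On a log scale the sampling SD is about 2% of RMSE, so a 95% interval is only about ±4%. That is fair. The primary model is written for untransformed troponin, where the ratio is larger, but its size depends on an assumed skew and should not be quoted as a property of this study.

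**The simple bootstrap is imperfect.** Resampling saved out-of-fold predictions gave nominal 95% intervals that covered about 87 to 88% for AUC, paired differences and calibration slope in simulation. A miss rate of 12 to 13% against 5% is more than slight. This is a reason to use a fuller method for the main models and to disclose the limit elsewhere. It is not a reason to report no interval.

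**Conclusion.** The point holds for the conventional models. The only planned spread is split variability. Calibration has no stated spread, and differences between hypotension definitions or nested models have no stated interval. For AUC, the split SD is roughly 3 to 4 times smaller than the sampling error that 75 events allow. The sampling error rests only on the event count and a range of AUC values; the split SD rests on simulation under assumed effects. For RMSE the ratio is about 8 to 10 on a log-type scale, and larger by an uncertain amount on raw troponin.

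A reader might infer that the validation itself is invalid. It is not: cross-validation by patient is sound and the point estimates stand. Nor is it a substantive defect that the plan does not say whether metrics are pooled or averaged over the five folds. In simulation the two AUCs differed by 0.703 − 0.695 = 0.008, less than one split SD (0.011), so this is a reporting detail. The gap should be closed before analysis.

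**What to change.** Add one paragraph to Model evaluation:

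1. Label the SD of RMSE and the distribution of AUCs over repetitions as split variability only, and say whether each metric is pooled or averaged over folds.
2. Report 95% intervals from resampling whole patients for RMSE, AUC, and calibration intercept and slope. Use the same resamples for both models when reporting a difference, so that the interval is paired.
3. For the a priori primary and secondary models, use a bootstrap that repeats the whole fitting and cross-validation procedure, with all copies of a patient kept in one fold. State that it may be conservative: in one simulation its AUC standard error was 0.045 against 0.037, which is indicative only.
4. For the many secondary and exploratory comparisons, a patient-level bootstrap of the out-of-fold predictions averaged over repetitions is enough. State that it holds the fitted models fixed and that nominal 95% intervals covered about 87 to 88% for AUC, paired differences and calibration slope in simulation.

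**Cost.** Item 4 needs no refitting. For item 3, 200 bootstraps × 5 repetitions × 5 folds = 5,000 fits per model, against the 100 × 5 = 500 already planned. The stated uncertainty will be wider. Cohort, data, models and point estimates do not change.

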For generalizability and to decrease bias, we will select features that are routinely collected. Non-vital sign candidate features include age, sex, urgent/emergent procedure (for the index surgery), postoperative GFR, and comorbidities within the RCRI categories.

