***A priori* features in the primary model**

This *a priori* list of predictors will be used for the primary modeling in Objective 1: duration hypotension (summarized as a percentage of duration of MAP<75 mmHg in the duration of time modeled, e.g. postoperative day 0, 1, and 2), age, sex, emergency surgery, RCRI, and postoperative GFR, as well as the postoperative day and the interaction between postoperative day and % duration MAP<75mmHg as detailed below.

Statistical analysis

Missing data

We will exclude patients with no intraoperative or postoperative vital signs and no troponin measurements from the cohort. Complete case analysis will be performed for vital sign features, with each complete case defined as a patient with ≥ 1 vital sign measurement(s) and ≥ 1 troponin measurement(s). Since the frequencies of measurements are different, missing vital signs are not considered missing values for inclusion/exclusion purposes as long as patients meet the complete case criteria. No imputation will be performed for vital sign data.

For features that are not vital signs (e.g. age, sex), we anticipate minimal missing data (as these variables are routinely collected), and assume missing at random. Due to the longitudinal data structure with correlated observations, we opted for a simpler method of imputation for the primary analysis. For features missing $< 1\%$, complete case analysis will be

performed; between 1-<10%, multiple imputation; above 10%, the feature would be excluded from the model and the reason for missing data will be investigated.

Data quality

The data quality of the CIHI vs. chart review results of the comorbidity information will be assessed by Pearson correlation, with chart review as the gold standard.

Cohort characteristics

Continuous data will be presented in mean (SD) if normal, and median (IQR) if non-normally distributed. Categorical data will be presented as frequency (%). The following characteristics will be presented as overall group, and stratified by MINS vs. no MINS:

- Age
- Gender
- American Society of Anesthesiologists' physical status classification (ASA)
- Type of anesthesia (general, neuraxial, peripheral, and/or sedation)
- RCRI score and categories: pre-existing TIA/CVA, insulin dependent diabetes, serum creatinine >177 mmol/L, coronary artery disease, congestive heart failure, and high risk surgery including intrathoracic, intraabdominal or suprainguinal vascular surgery

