The primary analysis will involve building a linear mixed effects model (with random intercepts) to predict the maximum daily troponin level between postoperative days 0 to 2 as the continuous outcome. The postoperative days 0, 1, and 2 accounts for approximately 40%, 40%, and 10% of MINS, respectively (4). Due to the limitations in retrospective data and the daily troponin monitoring, we will use day as a unit for time rather than hour to avoid overestimation of precision by readers.

For the primary and secondary models described in Objectives 1 and 2, an *a priori* list of predictors will be used: duration hypotension (summarized as a percentage of duration of MAP<75 mmHg in the duration of time modeled, e.g. postoperative day 1) age, sex, emergency surgery, RCRI, and postoperative GFR, as well as the postoperative day and the interaction between postoperative day and % duration MAP<75 mmHg as detailed below.

For longitudinal modeling, the vital signs data and troponin data will be aggregated to the day level, so that the model can predict at the daily temporal level. If there are multiple troponin measurements on the same day, the maximum will be taken. This aggregation of the data is necessary to account for the fact that the vital signs and troponin measurements are measured at irregular intervals (both across patients and data types), often due to the acting physician's response to the patient's condition. Additionally, due to this characteristic of the raw data, the vital signs predictors will be created such that they are standardized to be robust to the number of daily measurements performed (for example, by taking the percentage of day duration, NOT the total duration, of blood pressure below a specific threshold across all measurements during that day). A categorical time variable (representing the day of the measurement) will be included as a predictor within the model.

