Due to the longitudinal nature of the data, we need to include random effects to adjust for the dependence between within-patient daily observations. Thus, at minimum, we intend to include a random intercept corresponding to each patient within the model. However, we may consider including random slopes based on what is observed in the exploratory analysis of the vital signs data, though this would be limited by sample size. Since the effect of a vital signs covariate may be different depending on the day of monitoring, we will investigate interactions between the time predictor and vital signs predictors. This will be performed for only a small number of key time-varying predictors to avoid overfitting, given that the total

number of terms within the model will increase by at least 3 (if the interacting vital signs predictor is continuous or binary) for each additional interaction term included.

Visualizations of the effect of each predictor on the response will also be generated, to further investigate their relationships within the context of the model.

To summarize, a simplified example of the primary linear mixed effects model would be: $\text{Troponin} = \text{intercept} + b1\text{BP_day0} + b2\text{day1} + b3\text{day2} + b4\text{BP_day1*day1} + b5\text{BP_day2*day2} + \text{error}$ (plus other non-BP fixed-effect covariates as listed above). An example interpretation would be $b1$ will correspond to the effect of BP on Day 0, $b4$ will correspond to the additional effect of BP on Day 1 (with respect to Day 0) and $b5$ will correspond to the additional effect of BP on Day 2 (with respect to Day 0). However, we will perform exploratory analysis to explore other forms of longitudinal modeling to select the best model based on discrimination and calibration.

Survival analysis will not be employed due to the small variance in the days for the outcome (days 0-2). Also, right censoring is assumed in survival analysis, which does not apply in our case of troponin rise postoperatively as the majority of patients will not have a troponin increase eventually.

Secondary, Sensitivity, and Exploratory Analyses

In addition to the above outlined primary statistical analysis, we intend to conduct additional secondary, sensitivity and exploratory analyses to address Objectives 2 to 4 to examine how well the model performs given the following changes:

- Introduction of transformations or natural cubic splines on continuous predictors or outcomes

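### The binary model's cap of 8 variables is justified as about 10 events per parameter, but its eight listed items need 10 coefficients, or about 7.5 events each

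*Combined protocol and SAP*

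**What the plan says.** The section Parameter Count Based on Sample Size and Event Rate sets the plan's limits against overfitting. It counts coefficient terms for the linear mixed model and variables for the binary one: "at most 15 (i.e. 50 parameters per patient), and 8 variables for the generalized linear mixed effects models (i.e. 10 parameters per outcome event". It presents both limits as an aim and adds qualitative reasons, among them the repeated measures and the interest in interactions with time.

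Primary Modeling fixes one predictor list. It is introduced as applying "For the primary and secondary models described in Objectives 1 and 2", and Objective 2 is the daily probability of MINS or death. The items are percentage of time with MAP below 75 mmHg, age, sex, emergency surgery, RCRI, postoperative GFR, postoperative day, and "the interaction between postoperative day and % duration MAP<75 mmHg as detailed below". On the coding of day: "A categorical time variable (representing the day of the measurement) will be included as a predictor within the model". The worked equation in the same section, for days 0 to 2, has two day terms (b2, b3) and two interaction terms (b4, b5).

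The Population section expects 750 patients and about 75 events. The Outcome section keeps only a patient's first event, so the event count does not grow with the number of days modelled.

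**The concern.** A cap in variables and a ratio in parameters agree only if every variable takes one coefficient. Here two of the eight items take two each. The list therefore meets the cap of 8 when items are counted, but it does not deliver the ratio given as the reason for the cap.

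This ratio is the only figure the plan offers to show that the binary model is not too large for its data. A reader would carry it into a report as roughly 10 events per parameter, which the specified model does not have. In addition, both ratios name parameters per patient or per event. Taken literally, they describe a model with more parameters than data.

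**Working it through.** **Inputs.** 750 patients and about 75 events (Population); caps of 15 and 8 (Parameter Count); predictor list and categorical day (Primary Modeling); days 0, 1 and 2, hence three levels (Objectives 1 and 2).

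**The plan's own figures.**
- Linear model: 750/15 = 50 patients per coefficient. This reproduces exactly once the ratio is turned round. As printed, it would be 15/750 = 0.02 parameters per patient.
- Binary model: 75/10 = 7.5, rounded up to a cap of 8. At exactly 8 the ratio is 75/8 = 9.4 events per variable, so 10 holds only as a rounded figure. As printed, it would be 8/75 = 0.11 parameters per event.

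The division behind the caps is sound. The faults are the unit and the direction.

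**Coefficients in the listed binary model** (no intercept, no random-intercept variance):

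| Item | Coefficients |
|---|---|
| % duration MAP<75 | 1 |
| Age | 1 |
| Sex | 1 |
| Emergency surgery | 1 |
| RCRI (total score, as the Data Dictionary defines it) | 1 |
| Postoperative GFR | 1 |
| Postoperative day, 3 levels | 2 |
| Day x % duration MAP<75 | 2 |
| **Total: 8 items** | **10** |

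**Events per coefficient.** 75/10 = 7.5.

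**Both readings of the cap.**
- In variables: 8 items against 8, so the cap is met, but the ratio is 7.5 per parameter and not 10.
- In parameters: 10 against 8, so the cap is exceeded.

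**What 10 events per coefficient would need.** 10 x 10 = 100 events, which is 100/750 = 13.3% of patients. The plan's figure is 75/750 = 10%.

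**Primary linear model.** The same list gives 10 coefficients against a cap of 15, so it is within its limit.

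**How much the two extra coefficients matter.** Use the expected shrinkage S = 1 - p/LR, with LR = -750 ln(1 - R2 x 0.478). Here 0.478 is the maximum Cox-Snell R2 at 75 events in 750. The Nagelkerke R2 is an assumption, since the plan gives none, and patients are treated as single independent records. Going from 8 to 10 coefficients lowers S by 2/LR:
- R2 = 0.10: 0.054
- R2 = 0.15: 0.036
- R2 = 0.20: 0.027

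**The case against.** The strongest defence is that nothing is miscalculated. Read as events per variable, 8 variables at 75 events give 9.4, close to 10, and the list has 8 items. The fault is then one word plus an obvious inversion. The limit is only an aim, the model is secondary, and repeated patient-based cross-validation with calibration intercept and slope would show overfitting if it occurred. The event count is itself approximate: the introduction's 12-15% incidence applied to 750 patients gives 90 to 112.5 events, or 9.0 to 11.25 per coefficient.

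Much of this stands, and it sets the weight of the point. It does not remove the mismatch. The plan works with about 75 events, it names parameters, and its own equation writes the day and interaction terms out as separate coefficients.

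A reader might also infer more than the documents support:

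- *That RCRI may take five or six coefficients, giving 14 or 15 in all and 5.0 to 5.4 events each.* The wording "postoperative GFR, and comorbidities within the RCRI categories" comes from a list of candidate features, and "RCRI score and categories: pre-existing TIA/CVA, insulin dependent diabetes" from the descriptive table of cohort characteristics. The lists that govern the models say RCRI, and the Data Dictionary defines it as a total score.
- *That "number of terms within the model will increase by at least 3" contradicts a count of two interaction terms.* It fits days 0 to 2 as it stands: a new vital sign with its day interaction adds one main effect and two interaction terms.
- *That only 90% of the 75 events count, giving 67.5/10 = 6.75.* The Population section does not say whether its figure already refers to days 0 to 2.
- *That the binary model is seriously overfitted because of this mismatch.* The change in expected shrinkage is small. Most of the risk comes from the number of events, whichever way the cap is worded.

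**Conclusion.** The sentence is wrong as written for the binary model. The specified list has 10 fixed-effect coefficients and about 7.5 events for each at approximately 75 events. The stated ratio of 10 fails if the cap counts variables, and the cap of 8 fails if it counts parameters. The result rests on RCRI entering as a score, day having three levels, and the plan's own event estimate. The inverted ratios are clerical and change no number.

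Severity is minor. The primary model is unaffected, the binary model is secondary, and the planned validation covers the practical risk. Under the assumed R2 range, the two additional coefficients cost about 0.03 to 0.05 in expected shrinkage.

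**What to change.** State both caps in coefficients and turn both ratios round, for example: *at most 15 coefficients in the linear model (at least 50 patients per coefficient) and at most 10 coefficients in the binary model (about 7.5 outcome events per coefficient at approximately 75 events)*. Say that the count leaves out the intercept and the random-intercept variance.

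This changes one sentence of the analysis plan. It needs no new data and leaves both models as they are. The downside is a less favourable stated ratio.

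Dropping the interaction or penalising the binary model is optional and not part of this correction. Dropping the interaction would leave 8 coefficients and 75/8 = 9.4 events each, still short of 10, and would give up the day-specific hypotension effects that the plan names as an interest.
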